## **6.2.2. Attributing events to vaccine doses**

The dose relative to an event is the most recent study dose given to a participant prior to the start of a given event. For example, if the start date of an adverse event is between Dose 1 and Dose 2, the relative dose will be Dose 1.

If an event starts on the same day as a study dose, the relative dose will be derived from the additional information provided in the case report form (CRF) using the contents of the flag indicating if the event occurred before or after study dose. If ‘after study dose’ is selected, the relative dose for the event will be the one administered on the start day of the event. If ‘before study dose’ is selected, the relative dose for the event will be the dose prior to this one.

## **6.2.3. Handling of missing data**

### **6.2.3.1. Dates**

When partially completed dates (i.e. dates missing a day and/or month) are used in calculations, the following standard rules will be applied:

- A missing day will be replaced by 15
- A missing day and month will be replaced by June 30th.

The following exceptions apply:

- Adverse event start dates with missing day:
  - If the event starts in the same month as at least one of the study doses, the contents of AE.AESTRTPT (the flag indicating if the event occurred before or after study dose) will be used to complete the date. If ‘after study dose’ is selected, the imputed start date will match the first (or only) study dose given during that month. If ‘before study dose’ is selected, the imputed date will be one day before the first (or only) study dose given during that month.
- Adverse event start dates with missing day and month:
  - If the event starts in the same year as at least one of the study doses, the contents of AE.AESTRTPT (the flag indicating if the event occurred before or after study dose) will be used to complete the date. If ‘after study dose’ is selected, the imputed start date will match the first (or only) study dose given during that year. If ‘before study dose’ is selected, the imputed date will be one day before the first (or only) study dose given during that year.

All other cases of incomplete AE or concomitant medication/vaccination start date will follow the standard rules above.

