#### 214709 (RSV MAT-010) Protocol Amendment 3 Final

Type of contact	Visit 1	TC 1	Visit 2	TC 2	Comments
Time points	Day 1	Day 8	Day 31	Day 181	
Sampling time points	Pre-Vaccination	Post- Vaccination	Post- Vaccination	Post- Vaccination	
Distribution of e-diary device 	0				
Review of e-diary	0	0	0		
Return of e-diary device			0		
Collection of solicited adverse events (Days 1 to 7 post-vaccination) 6	0	0			[See Section 10.3.8 for more information]
Recording of unsolicited adverse events for 30 days (days 1 to 30 post vaccination)	•	•	•		[See Section 10.3.8 for more information]
Recording of AEs/SAEs leading to withdrawal	•	•	•	•	[See Section 10.3.8 for more information]
Recording of SAEs 	•	•	•	•	[See Section 10.3.8 for more information]
Recording of pregnancies		•	•	•	[See Section 10.3.8 for more information]
Recording of concomitant medications/vaccinations	•	•	•		[See Section 6.8 for more information]
Record any intercurrent medical conditions	•	•	•		[See Section 9.3.1 for more information]
Phone contact		•		•	
Investigator sign-off on eCRF before analysis			•	•	
COVID-19 eCRFs log page	•	•	•	•	
Screening Conclusion	•				
Study conclusion				•	[See Section 4.4 for more information]

TC= Telephone contact

• is used to indicate a study procedure that requires documentation in the individual eCRF.

o is used to indicate a study procedure that does not require documentation in the individual eCRF

 Date of birth (month and year or year only, as per local regulations), race, ethnicity and childbearing potential (if participant not of childbearing potential, the specific reason should be documented in the eCRF).

 Physical examination including (height and weight) BMI as well as resting vital signs (blood pressure, heart rate and respiratory rate, temperature) after at least 10 minutes of rest. At Day 1 (Visit 1) both physical exam and vital signs will be measured. At Day 31 (Visit 2) medical and vaccination history and vital signs may be measured.

 Only for women of childbearing potential. Urine pregnancy test is sufficient to determine the eligibility to enter the study. Serum pregnancy test (instead of urine test) may be performed if required by country, local or ethics committee regulations.

214709 (RSV MAT-010) Protocol Amendment 3 Final

 Fever is defined as temperature  $\geq$  38.0°C. The preferred location for measuring temperature in this study is the oral cavity.

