## **4.2. Primary Endpoint(s) Analyses**

### **4.2.1. Safety analysis**

The analysis of solicited administration site event (associated with RSV or Flu) and solicited systemic event will be performed on solicited safety set.

- The number and percentage with exact 95% CI of participants reporting each solicited administration site event (any grade, each grade) and solicited systemic event (any, each grade) during the 7-day follow-up period after dosing will be tabulated by maximum intensity per participant for each study group.
- For fever during the 7-day follow-up period after vaccination, the number and percentage of participants reporting any fever (i.e., temperature  $\geq 38$  °C) and fever by half degree (°C) cumulative increments, any Grade 3 fevers, will be reported.
- Duration in days of solicited administration site and systemic events within 7 days after vaccination will be tabulated by study group and overall. The derivation rule of duration in days for solicited events is detailed in section [6.2.4.9](#).

The analysis of unsolicited AEs and SAEs will be performed on ES.

- The number and percentage of participants reporting unsolicited AEs within 30 days after dosing with exact 95% CIs will be tabulated by group and by Medical Dictionary for Regulatory Activities (MedDRA) terms.
- Similar tabulations will be done for Grade 3 unsolicited AEs, for any causally related unsolicited AEs, and for Grade 3 related unsolicited AEs.
- The number and percentage of participants reporting at least one SAE within 30 days after dosing with exact 95% CIs will be tabulated by group and by MedDRA terms.
- The number and percentage of participants reporting at least one SAE up to study end with exact 95% CIs will be tabulated by group and by MedDRA terms.
- By-participant listings of SAEs, and AEs leading to study withdrawal will be prepared.

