### **6.2.4. Data derivation**

#### **6.2.4.1. Age at first dose in years**

When age at first dose is to be displayed in years, it will be calculated as the number of complete calendar years between the date of birth and the date of first dose. For example:

DOB = 10SEP1983, Date of first dose = 09SEP2018 -> Age = 34 years

DOB = 10SEP1983, Date of first dose = 10SEP2018 -> Age = 35 years

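### The SAP's fallback for incomplete adverse event start dates can move some events that began in Days 1-30 out of the primary 30-day safety tables

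*SAP*

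**What the plan says.** SAP Amendment 2, section 6.2.3.1, gives two standard rules: "A missing day will be replaced by 15" and "A missing day and month will be replaced by June 30" (30 June of the known year).

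Two exceptions protect AE start dates flagged as after the dose:
- Day unknown, same month as a study dose: "the imputed start date will match the first (or only) study dose given during that month".
- Day and month unknown, same year as a study dose: "the imputed start date will match the first (or only) study dose given during that year".

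Then comes the fallback: "All other cases of incomplete AE or concomitant medication/vaccination start date will follow the standard rules above". The section sets no upper limit at the end of the event, the last contact or the end of the collection window.

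Section 6.2.1 counts study day from the dose date, which is Day 1. Section 4.2.1 tabulates "The number and percentage of participants reporting unsolicited AEs within 30 days after dosing" and, likewise, SAEs within 30 days. The long SAE endpoint is Day 1 to Day 181 in SAP Table 1, but section 4.2.1 describes its table as running to study end.

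A related point concerns age. Footnote 1 of the Schedule of Activities in the protocol collects "Date of birth (month and year or year only, as per local regulations", while SAP 6.2.4.1 says of age that "it will be calculated as the number of complete calendar years between the date of birth and the date of first dose".

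**The concern.** The two halves of section 6.2.3.1 pull in opposite directions. In the dosing month or year, a partly dated event is placed on Day 1 and is certain to be counted. In the next month or year, an event just as likely to be in the window is placed mid-month or mid-year, wherever the window ends. A 30-day window nearly always runs into a second calendar month, so the second case is not exotic.

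Safety up to study end is a primary objective, raised to that level in Protocol Amendment 3. At stake are a few events missing from the primary 30-day counts, and some imputed onset dates that fall after the participant has left the study.

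**Working it through.** **Inputs.** Study day = onset date - dose date + 1 (SAP 6.2.1). Windows: Day 1-30 and Day 1-181 (SAP Table 1). Latest allowed last contact: Day 195 (Protocol Table 2). Day 1 is treated as the only study dose, because the optional Visit 2 influenza vaccination is outside the experimental design. Actual dose dates are not in the documents; vaccination had stopped by 1 March 2022 (Protocol 2.3). The plan gives no figure of its own to reproduce.

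**Day unknown, onset in the next month.** Take a dose on day d of a month with m days.
- The 15th of the next month is Day m + 16 - d. It exceeds 30 when d ≤ m - 15.
- The window reaches the next month when d ≥ m - 28, and then contains d + 29 - m days of it.
- So all next-month events are lost for doses on the 2nd-15th of a 30-day month, the 3rd-16th of a 31-day month, and the 1st-13th of February 2022.

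Example: dose 5 November 2021, onset 1 December = Day 27. The imputed date, 15 December, is Day 30 + 16 - 5 = 41.

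For all November doses, the lost onset days are 1 + 2 + ... + 14 = 105. The window holds 30 × 30 = 900 onset days, so 105/900 = 11.7%. Of next-month onset days alone (1 + ... + 29 = 435), the share is 105/435 = 24.1%.

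**Day and month unknown, onset in the next year.** 30 June 2022 is Day 182 for a dose on 31 December 2021, and later for any earlier dose. It is Day 196 for a dose on 17 December, so for doses up to that date it falls after the latest allowed last contact. All such events lie outside the 30-day tables. Only December doses from the 3rd to the 31st have January days in the 30-day window, again 435 onset days.

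**Share of in-window onset days dated outside Day 1-30**, with dose dates and onset days uniform over an assumed enrolment period:

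| Assumed dose dates | Day unknown | Day and month unknown |
|---|---|---|
| 1 Sep 2021-28 Feb 2022 | 630/5,430 = 11.6% | 435/5,430 = 8.0% |
| 1 Aug-31 Dec 2021 | 525/4,590 = 11.4% | 435/4,590 = 9.5% |
| 1 Oct-31 Dec 2021 | 315/2,760 = 11.4% | 435/2,760 = 15.8% |
| 1 Nov 2021-31 Jan 2022 | 316/2,760 = 11.4% | 435/2,760 = 15.8% |

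**Opposite error.** An SAE that began on Day 31-181 in the dosing year, with day and month unknown and flagged as after the dose, is dated Day 1 and enters the 30-day SAE table. Over the same four periods this applies to 14% to 48% of Day 31-181 onset days.

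**Alternative rule.** Imputing the later of the dose date and the first day of the known month (or 1 January of the known year) puts 0% of in-window onset days outside either window in every period. In the example it gives 1 December = Day 27.

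**Age.** With ages uniform over 18-49 and the standard imputation, a simulation computes 0.06% of women (birth month and year known) to 0.34% (year only) as outside 18-49. That is 0.0006 × 1541 ≈ 1 to 0.0034 × 1541 ≈ 5 women.

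**The case against.** Four stronger readings are tempting, and the documents do not support them.

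- *Partly dated in-window events drop out generally.* They do not. Both exceptions keep same-month and same-year events, and about 88% of in-window onset days with an unknown day stay in Day 1-30.
- *The long SAE table loses events too.* That needs a cut at Day 181 on the imputed date. Section 4.2.1 describes the table as running to study end, so a table of all collected SAEs would still count an event dated 30 June 2022. The Day 1-181 endpoint label leaves this unsettled.
- *Every recorded non-serious AE must have begun by Day 30, so the error runs one way.* The Schedule of Activities records AEs leading to withdrawal through Day 181, so a later onset can be genuine. For SAEs the rules also move late events to Day 1.
- *Imputed birth dates distort the main analyses.* The primary comparisons use unadjusted t-based intervals. Age category enters only optional ANCOVA models and a demographic table.

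The strongest general objection is rarity. Participants are contacted at Day 8 and Day 31, and SAEs are reported within 24 hours of awareness, so an onset in that window known only by year is implausible. The safety tables are descriptive, one rule serves all randomized groups, and nothing points to a between-group bias. This limits the importance of the point. It does not answer it, because the fallback still gives wrong dates whenever it is triggered.

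**Conclusion.** The point holds as a minor correction. The fallback in section 6.2.3.1 dates some AEs that began within Day 1-30, in the month after dosing, beyond Day 30, and so removes them from the primary 30-day tables. The share is about 11-12% of in-window onset days with an unknown day. That figure rests on uniform dose and onset dates, but barely moves across the enrolment periods tried. Events known only by a later calendar year always leave the 30-day tables. The effect on actual counts cannot be sized, because the number of partial dates is not given; it is probably small. Loss from the study-end SAE table remains conditional on a cut the SAP does not state.

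**What to change.** In SAP 6.2.3.1, replace the fallback for AE start dates as follows:

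1. Unless the event is flagged as before the dose, impute the later of the dose date and the first day of the known month (or 1 January of the known year).
2. Never impute a date after the AE end date or last contact.
3. State in 4.2.1 that the long SAE table counts every SAE collected to study end, whatever its imputed date.

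The cost is one paragraph and one derivation, extending the convention the SAP already uses for the dosing month. The downside is that a few later SAEs may enter the 30-day table. For example, an SAE from May 2022 known only as 2022, in a woman dosed on 15 December 2021, would be dated 1 January = Day 18. Flag imputed dates in the listings so that such cases are visible.

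Optional and minor: use the age recorded in the eCRF at Visit 1 (Protocol 8.2.1.2) for the code 2010 age check, rather than an age computed from an imputed birthday.

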### **6.2.3.2. Daily recording of solicited events**

#### **6.2.3.2.1. Studies with electronic diaries**

For studies using electronic diaries for the collection of solicited events, a solicited event will be considered present only when a daily recording of grade 1 or more is present.

### **6.2.3.3. Unsolicited adverse events**

Unsolicited adverse event summaries are including serious adverse events unless specified otherwise.

Missing severity, relationship with study vaccine, and outcome of unsolicited adverse events will not be replaced and will appear as 'UNKNOWN' when displayed in a statistical output.

### **6.2.4. Data derivation**

#### **6.2.4.1. Age at first dose in years**

When age at first dose is to be displayed in years, it will be calculated as the number of complete calendar years between the date of birth and the date of first dose. For example:

DOB = 10SEP1983, Date of first dose = 09SEP2018 -> Age = 34 years

DOB = 10SEP1983, Date of first dose = 10SEP2018 -> Age = 35 years

#### **6.2.4.2. Weight**

Weight will be presented in kilograms. Weights reported in pounds will be converted as follows:

Weight in kilograms = Weight in pounds / 2.2

#### **6.2.4.3. Height**

Height will be presented in centimeters. Heights reported in feet and inches will be converted as follows:

Height in centimeters = Height in inches x 2.54

#### **6.2.4.4. Body mass index (BMI)**

BMI will be calculated as follows:

BMI = (Weight in kilograms) / (Height in meters)

#### 6.2.4.5. Temperature

Temperatures will be presented in degrees Celsius (°C). Temperatures reported in degrees Fahrenheit (°F) will be converted as follows:

$$\text{Temperature (Celsius)} = ((\text{Temperature (Fahrenheit)} - 32) \times 5)/9$$

#### 6.2.4.6. Numerical serology results

Numerical serology results will be derived from the content of IS.ISORRES in the SDTM dataset. For assays with a specific cut-off, the following derivation rules apply:

IS.ISORRES	Derived value
“NEG”, “-”, or “(−)”	cut-off/2
“POS”, “+”, or “(+)”	cut-off
“< value” and value is <= assay cut-off	cut-off/2
“< value” and value is > assay cut-off	value
“> value” and value is < assay cut-off	cut-off/2
“> value” and value is >= assay cut-off	value
“value” and value is < cut-off	cut-off/2
“value” and value is >= cut-off	value
All other cases	missing

The cut-off tests for immunogenicity evaluation will be as per following:

System	Component	Method	Unit	Cut-off (LLOQ)	ULOQ
Serum	RSV-A Neutralising Antibody	NEUTRALISATION	ED60	18	123535
Serum	RSV-A Neutralising Antibody	NEUTRALISATION	IU/mL	56	217400
Serum	RSVPreF3 IgG antibody concentrations	ELISA	EU/mL	25	251769
Serum	RSV-B Neutralising Antibody	NEUTRALISATION	ED60	30	138336
Serum	RSV-B Neutralising Antibody	NEUTRALISATION	IU/mL	44	171279
Serum	A/Victoria/2570/2019 (H1N1)	HI assay	TBD	TBD	TBD
Serum	A/Tasmania/503/2020 (H3N2)	HI assay	TBD	TBD	TBD
Serum	B/Washington/02/2019	HI assay	TBD	TBD	TBD
Serum	B/Phuket/3073/2013	HI assay	TBD	TBD	TBD

Note: the assay cut-off (LLOQ), ULOQ and units may be further adjusted at time of analysis when notified by the lab.

#### 6.2.4.7. Geometric mean titres (GMTs) and concentrations (GMCs)

Geometric Mean Titre (GMT) or Concentration (GMC) calculations are performed by taking the inverse logarithm of the mean of the log titre or concentration transformations. Non quantifiable antibody titres or concentrations will be converted as described in section 6.2.4.6 for the purpose of GMT/GMC calculation. The cut-off value is defined by the laboratory before the analysis.

#### **6.2.4.8. Onset day**

The onset day for an event (e.g. AE, concomitant medication/vaccination) is the number of days between the last study dose and the start date of the event. This is 1 for an event occurring on the same day as a study dose (and reported as starting after study dose).

#### **6.2.4.9. Duration of events**

The duration of an event with a start and end date will be the difference between the start and end date plus one day, i.e. an event that starts on 03MAR2018 and ends on 12MAR2018 has a duration of 10 days.

The duration of solicited events will be calculated as the sum of the individual days with the adverse event reported at grade 1 or higher during the solicited event period.

#### **6.2.4.10. Counting rules for occurrences of solicited events**

When the occurrences of solicited events are summarized, each event recorded as having occurred during a specific period will be counted as only one occurrence regardless of the number of days on which it occurs. Also, in the case of co-administered study interventions, an administration site event recorded for a participant following multiple study interventions will be counted as only one occurrence.

### **6.2.5. Display of decimals**

#### **6.2.5.1. Percentages**

Percentages and their corresponding confidence limits will be displayed with one decimal except for 100% in which case no decimal will be displayed.

#### **6.2.5.2. Differences in percentages**

Differences in percentages and their corresponding confidence limits will be displayed with two decimals.

#### **6.2.5.3. Demographic/baseline characteristics statistics**

The mean, median, and standard deviation for continuous baseline characteristics (height, weight, body mass index (BMI), pre-dose body temperature) will be presented with one decimal.

The minimum and maximum values and quartile values (if required) will be presented with the same number of decimals as the observed values.

The maxima and minima of transformed height/weight variables will be displayed without decimals.

The maximum and minimum of transformed body temperatures will be displayed with one decimal.

#### 6.2.5.4. Serological summary statistics

The number of decimals used when displaying geometric mean titers (GMT) or concentrations (GMC) and their confidence limits is assay specific based on the magnitude of the assay result post-dose and the clinically relevant assay threshold. The same number of decimals will be used for a given assay regardless of the timepoint presented.

Lowest clinically relevant threshold	Example	Number of decimals to display
<0.3	Diphtheria, tetanus, anti-PRP	3
>=0.3 and <4	Streptococcus pneumoniae , Meningococcal bactericide	2
>=4 and <1000	Measles, rubella, varicella, polio	1
>=1000	CMI	0

GMT/GMC fold increase from pre-dose follows the same principle. Namely when the lowest clinically relevant threshold is 2 fold, 2 decimals are displayed while when the lowest clinically relevant threshold is 4 fold, 1 decimal is displayed.

GMT or GMC group ratios and their confidence limits will be displayed with 2 decimals regardless of the actual values.

## Version history

SAP Version	Approval Date	Protocol Version (Date) on which SAP is Based	Change	Rationale
SAP	29 Jun 2021	Amendment 1 (27 May 2021)	Not Applicable	Original version
Amendment 1	29 Mar 2022	Amendment 2 (17 November 2021)	
 
1. Blinding strategy detail from the study title has been deleted, as they vary between the lot to lot and co-administration groups.
 
2. Interim analysis has been removed.
 
3. Components updated with 2021/22 season Flu strains.
 
	
 
1. It was identified that the intervention type amongst the co-administration groups can be determined by the blinded site and sponsor staff using available information in the electronic case report forms (eCRF), therefore the blinding strategy was adapted to single-blind design for the co-administration groups.
 
2. The decision was made to not go forward with the BLA filing for the RSV Maternal vaccine, and as a result, the interim analysis was removed.
 
3. New information made available on the Flu strains.
 

## 1. INTRODUCTION

The purpose of this SAP is to describe the planned analyses for RSV MAT-010 (214709). Details of the planned analysis are provided.

### 1.1. Objectives, Estimands and Endpoints

**Table 1 Study objectives, endpoints and estimands**

Objectives	Endpoints/Estimands
Primary	
Safety 
 
To evaluate the safety and reactogenicity of RSVPreF3 when given alone (pooled lots) or co-administered with Flu D-QIV up to Day 31 post administration.
 
	
The number and percentage of participants in each group reporting
 
 
Each solicited administration site AE collected during the 7 days follow-up period (Day 1 to Day 7)
 
Each solicited systemic events in the 7 days follow-up period
 
Unsolicited AEs collected during the 30 days follow-up period (Day 1 to Day 30)
 
SAEs in the 30 days follow-up period (Day 1 to Day 30)
 

Immunogenicity 
 
To demonstrate the lot-to-lot consistency of 3 lots of the investigational RSVPreF3 vaccine based on GMC of RSVPreF3 IgG ELISA at Day 31
 
To demonstrate non-inferiority of Flu D-QIV vaccine when co-administered with RSVPreF3 vaccine compared to Flu D-QIV given alone based on Geometric mean titer (GMT) of Flu D-QIV antibody titers against 4 influenza strains at Day 31 post administration
 
	
RSVPreF3 IgG ELISA concentration at Day 31 (30 days post administration)  Measured by ratio of Geometric mean concentration (GMC) between lots in terms of RSVPreF3 IgG ELISA titers at Day 31 (30 days post administration)
 
Flu D-QIV antibody titers against 4 influenza strains at Day 31 (30 days post administration)  Measured by ratio of Haemagglutinin inhibition (HI) GMT between group of Flu D-QIV vaccine co-administered with RSVPreF3 vaccine and Flu D-QIV vaccine alone group against 4 strains at Day 31 (30 days post administration)

Secondary	
Secondary Safety	

 
To evaluate the safety of RSVPreF3 when given alone and co-administered with Flu D-QIV from vaccination up to study end.
 
	
The number and percentage of participants reporting SAEs from first vaccination up to study end. [Day 1 to Day 181]

Confirmatory Immunogenicity***	

 
To demonstrate the non-inferiority of RSVPreF3 vaccine co-administered with Flu D-QIV compared to given alone based on GMT of RSV A neutralizing antibody at Day 31 post administration
 
To demonstrate the non-inferiority of Flu D-QIV vaccine co-administered with RSVPreF3 compared to given alone based on Seroconversion rate
 
	
RSV A neutralizing antibody titers at Day 31 (30 days post administration)  Measured by ratio of GMT between group of RSVPreF3 vaccine co-administered with Flu D-QIV and RSVPreF3 vaccine alone (pooled lot 1,2,3) group in term of RSV A neutralizing antibody titers at Day 31 (30 days administration)
 
 
Seroconversion rate to Flu D-QIV HI antibody titers against the 4 influenza strains at Day 31
 

Objectives	Endpoints/Estimands
(SCR**) of Flu D-QIV HI antibody titers against 4 influenza strains at Day 31 post study intervention	Measured by the difference of proportion of participants achieving seroconversion for HI antibody at Day 31 in the group of Flu D-QIV vaccine co-administered with RSVPreF3 vaccine and the group of Flu D-QIV vaccine alone
Descriptive Immunogenicity	

 
To evaluate the humoral immune response of RSVPreF3 vaccine when given alone and co-administered with Flu D-QIV in terms of RSV A, RSV B neutralizing antibody and RSVPreF3 IgG concentration at Day 1 (prior to the vaccination) and Day 31 (post study intervention).
 
	
 
RSV A, RSV B neutralizing antibody titers and RSV PreF3 IgG concentration at Day 1 and Day 31
 
 
GMT of RSV A and RSV B neutralizing antibody, GMC of RSVPreF3 IgG at Day 1 and Day 31, in the group of RSVPreF3 vaccine co-administered with Flu D-QIV and the group of RSVPreF3 vaccine alone

 
To evaluate the humoral immune response to the Flu D-QIV vaccine when given alone and co-administered with RSVPreF3 vaccine in terms of antibody titers against 4 influenza strains at Day 1 and Day 31
 
	
Flu D-QIVHI antibody titers against the 4 influenza strains at Day 1 and Day 31
 
HI GMT in the 4 influenza strains at Day 1 and Day 31 in the group of Flu D-QIV vaccine co-administered with RSVPreF3 vaccine and the group of Flu D-QIV vaccine alone


 
To evaluate seroprotection rate (SPR)* and Seroconversion rate (SCR)** of the Flu D-QIV vaccine when given alone and co-administered with RSVPreF3 vaccine
 
	
Seroprotection rate to Flu D-QIV HI antibody titers against the 4 influenza strains at Day 1 and Day 31
 
Measured by the proportion of participants achieving an HI antibody titer <math>\geq 1:40</math> at Day 1 and Day 31 in the group of Flu D-QIV vaccine co-administered with RSVPreF3 vaccine and the group of Flu D-QIV vaccine alone
 
 
Seroconversion rate to Flu D-QIV HI antibody titers against the 4 influenza strains at Day 31
 
 
Measured by the proportion of participants achieving seroconversion for HI antibody at Day 31 in the group of Flu D-QIV vaccine co-administered with RSVPreF3 vaccine and the group of Flu D-QIV vaccine alone

 
To evaluate the humoral immune response in 3 individual lots of RSVPreF3
 
	
 
RSV A, RSV B neutralizing antibody titers and RSVPreF3 IgG antibody concentrations at pre-vaccination and Day 31
 
 
Geometric mean titer/concentration (GMT/GMC) in term of RSV A, RSV B neutralizing antibody and RSVPreF3 IgG antibody at Day 1 (pre-vaccination) and Day 31 in each of 3 lots of the investigational PreF3 vaccine.

Tertiary Objective	
CCI	

[figure not shown]
\*SPR is defined as the percentage of vaccines with a serum HI titer  $> 1:40$  that usually is accepted as indicating protection.

\*\* The SCR is defined as the proportion of participants with:

A Day 1 (pre-vaccination) serum anti-HI titer  $< 1:10$  and a Day 31 (post-vaccination) serum anti-HI titer  $\geq 1:40$ , or  
A Day 1 (pre-vaccination) serum anti-HI titer  $\geq 1:10$  and a fold increase (post/pre)  $\geq 4$  at Day 31

\*\*\* Two confirmatory objectives will be tested sequentially.

